8 DATA HANDLING AND QUALITY ASSURANCE

8.1 Data Management

Data management based on GCP refers to the activities defined to achieve safe routines to efficiently enter patient information into a database, avoiding errors.

The data management routines include procedures for handling of CRF, eCRF and database set-up and management, data entry, data verification and validation (quality control of database), and documentation of the performed activities, including information of discrepancies in the process. The eCRF/ data entry screens, and the database/programs will be designed in accordance with the CIP and LINK standard operating procedure (SOP) system.

8.1.1 Data Collection

The clinical investigation data will be collected via eCRF completed by the Investigator or other qualified personnel at the site, and by the Clinical Trial Unit. Together these constitute a remote electronic data system, which complies with the associated requirements of EN ISO 14155:2011.

8.1.2 The Web-Based Case Report Form

Clinical data (including AEs and concomitant medications) will be entered into a 21 CFR Part 11-compliant eCRF (Viedoc4™). The eCRF includes password protection and internal quality checks, such as automatic range checks, to identify data that appear inconsistent, incomplete, or inaccurate. Clinical data will be entered directly from the source documents, unless the eCRF is considered source.

Authorized trial site personnel designated by the Investigator will complete data collection. Appropriate training and security measures will be completed with the Investigator and all authorized trial site personnel prior to get access to live version of the eCRF and any data being entered into the system for any trial patient.

The CRF specification provided in this CIP will be the basis for the set-up of the eCRF in Viedoc4™. However minor deviations might be necessary due to technical issues that cannot be foreseen during the CIP writing process.

8.1.3 The Entering of Data into the Electronic Case Report Form

The eCRFs should always reflect the latest observations on the patients participating in the trial. Therefore, the eCRFs should be completed as soon as possible during or after the patient's visit. The Investigator must verify that all data entries in the eCRFs are accurate and correct. If some assessments are not done, or if certain information is not available, not applicable or unknown, the Investigator should indicate this in the eCRF. The Investigator will be required to electronically sign off all collected data.

8.1.4 The Query Process

The Monitor will review the eCRFs and evaluate them for completeness and consistency. Each eCRF will be compared with the respective source documents to ensure that there are no discrepancies between critical data. All entries, corrections, and alterations are to be made by the Investigator or authorized designee. The Monitor cannot enter data in the eCRFs. Once

clinical data have been submitted to the central server via the eCRF, corrections to the data, made by the site personnel, will be audit trailed, meaning that the reason for change, the name of the person who made the change, together with date and time will be logged. Roles and rights of the site personnel responsible for entering clinical data into the eCRF will be determined in advance. If additional corrections are needed, the responsible Monitor or Data Manager will raise a query in the eCRF. The appropriate investigational personnel will answer the queries in the eCRF.

8.1.5 Signing of Data

Electronic CRF records will be automatically appended with the identification of the creator, by means of their unique User ID. Specified records will be electronically signed by the Investigator to document his/her review of the data and acknowledgement that the data are accurate. This will be facilitated by means of the Investigator's unique User ID and password. Date and time stamps will be added automatically at time of electronic signature.

8.1.6 Database Lock

All changes will be fully recorded in a protected audit trail, and a reason for the change will be required. Once all data have been entered, verified, and validated; and all queries are solved, medical coding approved, and SAE reconciliation performed; the database will be locked.

8.2 Patient Records and Source Data

The data may be recorded directly in the eCRF, which will then be considered as source data. The origin of source data in the investigation will be further specified in a separate document ("Origin of Source Data").

It is the responsibility of the Investigator to record essential information in the medical records in accordance with national regulations and requirements, including, but not limited to:

- Study code,
- Patient screening number and/or patient number,
- That informed consent for participating in the study was obtained, signed and dated by subjects,
- All visits during the investigation period,
- All AEs/ADEs, SAEs/SADEs, and
- Treatments and medications.

The Investigator is responsible for ensuring the accuracy, completeness, legibility, and timeliness of the data recorded in the CRFs.

8.3 Record Retention

The Investigator will retain copies of the records for a period of 15 years from the Close-out Visit. The Investigator must take measures to prevent accidental or premature destruction of these documents. In all cases, the Investigator must contact the Sponsor prior to disposing of any records related to the clinical investigation. Included in records to be retained are the

patients' medical records, signed CIP, copies of paper CRFs (if applicable), signed ICFs, IEC approval letters, product accountability records, correspondence concerning the clinical investigation, and any other documents to identify the patients (including the Patient Identification Log). The electronic data retention period is of at least 15 years. Archiving of data is performed according to industry standards such as in PDF/A format.

In addition, if the Investigator is no longer able to fulfill the role of Investigator (e.g. if he/she retires), a new Investigator will be appointed in consultation with the Sponsor.

8.4 Monitoring, Audits, and Inspections

During the investigation, the Monitor will have regular contacts with the investigational site. These contacts will include visits to confirm that the facilities remain adequate to specified standards and that the investigational team are carrying out the procedures stated in the CIP. All data must be accurately recorded in the eCRF and source data verified (comparison of eCRF data with the patient's medical records and other records at the investigational site). The eCRF and other records must be accessible during the visit.

The Monitor or other Sponsor personnel will be available between visits if the Investigator or other staff at the site needs information or advice.

Authorized representatives of the Sponsor or RA may visit the site to perform audits or inspections, including source data verification.

8.5 Training of Staff

A delegation log will be completed for each investigational site team member to indicate which activities the Investigator has authorized them to perform. This must be updated prior to a new or existing team member undertaking any new responsibility.

The Investigator will ensure that appropriate training relevant to the clinical investigation is given to the medical, nursing and other staff involved and that new information of relevance to the performance of this clinical investigation is forwarded to the staff involved.

9 STATISTICAL METHODS AND PLANNED ANALYSIS

The statistical planning, analysis and reporting work will follow LINK SOP system. All analyses described below will be performed using SAS Version 9.4.⁴⁰

For continuous data, number of missing and non-missing records, mean, standard deviation, median, 25th and 75th percentiles, minimum and maximum will be presented. All mean, median, confidence interval (CI), and standard deviation (SD) values will be formatted to one more decimal place than the measured value. Minimum and maximum values will be presented with the same number of decimal places as the measured value. Categorical data, including both nominal and ordered variables, as well as binary variables, will be presented by frequencies and percentages. Percentage values will be presented with 1 decimal place. In case of any hypothesis testing, p-values will be presented using a maximum of 4 decimal places.

The statistical analysis will be based on the observed data. However, if missing data, due to patient withdrawals or other reasons, or outliers, are considered to be an issue, measures will be taken in order to reduce bias or, in case bias is unavoidable, conservatively direct the bias.

Details on the presentation of descriptive statistics, analytical methods, and handling of statistical issues will be given in the statistical analysis plan (SAP).

9.1 Statistical Analysis

The clinical performance endpoints will be presented with the appropriate point estimate together with the 95% confidence interval. Any possible statistical testing will be performed using an overall significance level of 5%.

Although there are two co-primary endpoints, no adjustment of e.g. p-values or confidence intervals will be applied. This is for two reasons, the first being that the evaluation of the second co-primary endpoint (safety and tolerability) will only be based on descriptive statistics and data listings, and the second is that both co-primary endpoints have to show favorable results. For all other statistical analyses of the secondary endpoints, no adjustment due to multiple testing will be performed.

Statistical analysis will be based on all data, however, results will also be presented by site.

If the stated assumptions that the statistical evaluation is built upon can be questioned, suitable alternative methods may be applied. For example, a 95% confidence interval based on a non-parametric method may be applied if assumption of data belonging to the normal distribution seems not to hold. This, together with further details on the statistical analysis and identification of any possible exploratory or subgroup analysis, will be given in the SAP.

Sensitivity analyses may be performed to evaluate the robustness of the results.

Any deviations or changes to the study protocol specified statistical analyses will be documented and justified in the SAP and the Clinical Investigation Report (CIR).

9.1.1 Analysis Data Sets and Populations

The two different analysis datasets that will be considered for analysis is as below:

Full Analysis Set (FAS): This is the primary population and comprises all patients entering the study and having received at least 1 dose of study treatment. Analyses of clinical performance will be performed against this population.

Per Protocol (PP) Population - This will include all FAS patients without any major protocol deviation, i.e. patients who have completed the study and sufficiently complied with the study protocol, have available primary endpoint data and have received the study treatment according to protocol. The final definition of a major protocol deviation will be decided and defined at the clean file meeting. If a relevant number of patients are excluded from the PP population, then selected outputs will be provided for the PP population.

All safety analyses will be performed against the FAS. All patients included in the FAS will be accounted for, including those who did not complete the study along with the reasons for withdrawal.

Subject disposition table presenting the number and percentage of patients reaching each study milestone will be reported. The reasons for withdrawal from the study will be tabulated.

Patients who not qualify for the FAS population will be listed.

9.1.2 Demographic and other Baseline Characteristics

All demographic and other baseline data will be summarized descriptively. Demographic and baseline assessments will be presented descriptively using the principles stated in [Section 9](#) above.

Medical history will be coded according to MedDRA classification and will be presented by system organ class and preferred term as part of the baseline data.

Prior or concomitant medications will be coded using WHODD and summarized by ATC class.

Prior medications will be identified as those with a start date before Day 0 and will be presented as part of the baseline data. The concomitant medications will be defined as those with a start date equal to or after Day 0.

9.1.3 Exposure to Treatment

Treatment compliance data, see [Section 5.8](#), will be presented descriptively.

9.2 Primary and Secondary Endpoints Analysis

9.2.1 Primary Endpoints Analysis

- Clinical cure rate on Day 7 will be calculated and presented together with a one-sided 95 % confidence interval based on the exact binomial distribution.
- Safety and tolerability will be assessed according to [Section 9.2.3](#).

9.2.2 Secondary Endpoints Analysis

Below is the list of all secondary endpoints (highlighted in italics) and other related variables, together with information on variable types, followed by additional information on the planned statistical analysis and presentation of the endpoints. Note that the analyses of the secondary endpoints will be performed on different patient categories as described in [Section 2.2](#).

- a) *Proportion endpoints* (based on values yes/no on the individual level, i.e. binary variables)
- b1) Bacterial Vaginosis symptoms: fishy smell (can take integer values in the interval 0-3)
- b2) Bacterial Vaginosis symptoms: burning (can take integer values in the interval 0-3)
- b3) Bacterial Vaginosis symptoms: irritation (can take integer values in the interval 0-3)
- b4) Sum of all BV symptoms score (can take integer values in the interval 0-9)
- c) *Cure rate on Day 14* (based on values yes/no on the individual level, i.e. binary variable)
- d) *Change in sum of all BV symptoms score* (can take values from -9 to +8)
- e) *Recurrence rates* (based on values recurrence=yes/no on the individual level, i.e. a binary variable)
- f) *Usability, measured by patient questionnaire* (the questionnaire contains 4 specific yes/no (i.e. binary) variables, and a 5th question, “How do you generally regard the treatment?”, rated on a 1-10 integer scale).

In summary, the secondary endpoints:

- a), c), e), and the first 4 questions in f) are considered as binary variables
- d), and the 5th question in f) are considered as continuous variables

The binary endpoints categorized as a), c), and e) above, will be calculated and presented together with a two-sided 95 % confidence interval based on the exact binomial distribution.

Two-sided 95% confidence intervals will be presented for endpoint d) using a parametric method assuming normally distributed data, i.e. arithmetic mean will be presented together with the 95% confidence limits.

Further, all study endpoints (primary, secondary, and exploratory), as well as the related variables specified in the list above, will be presented descriptively.

9.2.3 Tolerability and Safety Analysis

As part of the local tolerability and safety assessments, the following will be evaluated:

- Tolerability,
- Adverse events and SAEs, and
- Rate of withdrawals from the study and/or the study treatment.

9.2.3.1 Local Tolerability

Based on AEs.

9.2.3.2 Adverse Events

The AEs will be presented descriptively by means of frequency and percentages to evaluate both the rate of incidence and event occurrence among the different treatment groups. The descriptive tables will be presented with respect to intensity, seriousness, and relationship to the treatment.

9.3 Sample Size Determination

Assuming the true cure rate is equal to 70 %, 22 patients are needed to obtain 90 % chance (90 % power) to show that the one-sided 95 % CI for the observed cure rate is above 40 %. To compensate for a small number of non-evaluable patients, 24 patients will be included.

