- Recurrence rate on Day 14 and Day 35, defined as the proportion of patients clinically cured on Day 7 and thereafter responding “yes” to a yes/no question from the patient questionnaire on whether the symptoms have recurred

For patients receiving prolonged treatment

- Proportion of patients receiving prolonged treatment
- Clinical cure rate on Day 14, defined as the absence of all of the 3 Amsel criteria as defined above
- Proportion of patients being negative for each of the 3 Amsel criteria on Day 14 compared to Day 0
- Proportion of patients having a reduction in the sum of the 3 BV symptoms scores (fishy smell, burning, and irritation) on Day 11, Day 14, Day 21, and Day 42, compared to Day 0
- Change in the sum of the 3 BV symptoms scores (fishy smell, burning, and irritation) from Day 0 to Day 11, Day 14, Day 21, and Day 42
- Recurrence rate on Day 21 and Day 42, defined as the proportion of patients clinically cured on Day 14 and thereafter responding “yes” to a yes/no question from the patient questionnaire on whether the symptoms have recurred
- Proportion of patients receiving rescue treatment on Day 14

Exploratory endpoint variables:

All patients

- Effect on vaginal microbiome on Day 0 and Day 7
- Vaginal pH on Day 7

For patients not receiving prolonged treatment

- Effect on vaginal microbiome on Day 35

For patients receiving prolonged treatment

- Effect on vaginal microbiome on Day 14 and Day 42

Safety and Tolerability Endpoints:

See above, safety and tolerability, based on reported treatment-emergent AEs.

Statistical Methods:

Sample size (n=24) is based on having 90 % power to show that the one-sided 95 % confidence interval for the observed cure rate is above 40 %, assuming the true clinical cure rate, as defined in this study, to be equal to 70 % in this patient population.

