7.9.1 Primary endpoints

- Clinical performance endpoint: Clinical cure rate on Day 7 will be calculated and presented together with a one-sided 95 % confidence interval based on the exact binomial distribution (Clopper-Pearson).
- Clinical safety endpoint: Safety and tolerability will be assessed according to Section 7.10.2.

The primary clinical performance endpoint is the Clinical cure rate on Day 7, where clinical cure is defined as the absence of all of the Amsel criteria stated in [Section 3.1.1](#) above. The primary performance objective of the trial is to show that the Clinical cure rate is above 40 %, *i.e.* to show that the lower limit of the one-sided 95 % CI for the observed cure rate is above 40 %.

Hypotheses for the primary clinical performance endpoint

Null hypothesis: Clinical cure rate is less than or equal to 40 %.

Alternative hypothesis (one-sided): Clinical cure rate is above 40 %.

The primary clinical safety endpoint, i.e. safety and tolerability based on reported treatment-emergent AEs, will be analysed descriptively only, see Section 7.10.2 below, and will thus not be connected to any formal hypothesis testing.

7.9.2 *Secondary clinical performance endpoints*

The secondary clinical performance endpoints are either binary or continuous.

The usability data, as measured by the patient questionnaire and which contain both binary and continuous endpoints, will only be presented descriptively.

The other binary secondary clinical performance endpoints will be calculated and presented together with a two-sided 95 % confidence interval based on the exact binomial distribution (Clopper-Pearson). No hypothesis testing will be made on the binary endpoints.

The only remaining clinical performance endpoint that is considered as a continuous endpoint is the change in the sum of the 3 BV symptoms scores. Here, applying Student's t distribution, a two-sided 95% confidence intervals for the arithmetic mean will be presented.

Hypothesis for the continuous secondary clinical performance endpoint "Change in the sum of the 3 BV symptoms scores"

Null hypothesis: Change from baseline is = 0.

Alternative hypothesis (two-sided): Change from baseline \neq 0.

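### The 90 % power claim does not hold for the planned exact analysis: 22 evaluable patients give 81.4 % and 24 give 84.7 %

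*Protocol*

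**What the plan says.** Protocol 9.3 starts from "Assuming the true cure rate is equal to 70" % and concludes that "22 patients are needed to obtain 90 % chance (90 % power") to place the one-sided 95 % interval above 40 %. It then adds: "To compensate for a small number of non-evaluable patients, 24 patients will be included". SAP 5.1 repeats this. The Protocol synopsis, under Statistical Methods, puts it differently: "Sample size (n=24) is based on having 90 % power", with no mention of 22.

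The analysis is fixed elsewhere. Protocol 9.2.1 has the Day 7 cure rate "presented together with a one-sided 95 % confidence interval based on the exact binomial distribution". SAP 7.9.1 names the method, a "one-sided 95 % confidence interval based on the exact binomial distribution (Clopper-Pearson"), and sets the hypothesis, "Null hypothesis: Clinical cure rate is less than or equal to 40" %. Its success criterion is "to show that the lower limit of the one-sided 95 % CI for the observed cure rate is above 40" %. Neither document says which method produced the 22.

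**The concern.** A power figure should describe the test that will be run. The exact interval guarantees its coverage by being conservative, and with about two dozen patients the discreteness of the counts makes that conservatism large. A sample size from a smooth normal formula can then overstate the chance of success by several points.

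This is the only analysis in the trial with a power claim, and it carries a formal null hypothesis and a pass/fail threshold. If the claim is too high, the sponsor, the ethics committee and later readers of a negative result are given too low a risk that an effective product fails. There is also an inconsistency over which n the 90 % belongs to, 22 or 24.

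**Working it through.** **Inputs.** True cure rate p1 = 0.70 (Protocol 9.3, SAP 5.1). Reference rate p0 = 0.40, one-sided 5 %, Clopper-Pearson lower limit above 0.40 (SAP 7.9.1). Evaluable n = 22, 24 enrolled (Protocol 9.3).

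**Step 1. Reproduce the 22.** The usual normal-approximation formula is

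n = [(z₀.₉₅ √(p0(1−p0)) + z₀.₉₀ √(p1(1−p1))) / (p1 − p0)]²

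= [(1.645 × √0.24 + 1.282 × √0.21) / 0.30]² = [(0.806 + 0.587) / 0.30]² = 21.56, rounded up to 22.

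The same approximation gives 90.5 % power at n = 22. The figure is right for that formula, which is its apparent source.

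**Step 2. Find the exact success rule.** The one-sided 95 % Clopper-Pearson lower limit for x cures of n is the 5 % quantile of a Beta(x, n − x + 1) distribution. It exceeds 0.40 exactly when P(X ≥ x | n, 0.40) < 0.05.

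- n = 22: 13 cures give a lower limit of 39.5 % (fail); 14 give 43.9 % (success).
- n = 23: 13 cures give 37.5 % (fail); 14 give 41.7 % (success).
- n = 24: 14 cures give 39.7 % (fail); 15 give 43.7 % (success).

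**Step 3. Exact power** = P(X ≥ cut-off | n, 0.70).

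| Evaluable n | Cures needed | Attained type I error | Power at 70 % | Risk of missing the objective |
|---|---|---|---|---|
| 22 | 14 | 2.15 % | 81.4 % | 18.6 % |
| 23 | 14 | 3.49 % | 88.0 % | 12.0 % |
| 24 | 15 | 2.17 % | 84.7 % | 15.3 % |
| 25 | 15 | 3.44 % | 90.2 % | 9.8 % |
| 26 | 16 | 2.17 % | 87.5 % | 12.5 % |
| 27 | 16 | 3.37 % | 92.0 % | 8.0 % |

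Power does not rise steadily with n, because the cut-off moves in whole patients. The smallest n reaching 90 % is 25. It falls below again at 26 and stays above from 27.

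**Step 4. Where 90 % would come from.** Counting 13 of 22 as success gives power of 90.8 %, but that rule has an exact type I error of 5.5 % and a lower limit of 39.5 %. The SAP's own criterion calls 13 of 22 a failure.

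**Step 5. True rate needed for 90 %.** With the exact rule, 90 % power requires a true cure rate of about 73.6 % at n = 22, 71.0 % at n = 23 and 72.3 % at n = 24.

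**Step 6. Missing Day 7 results.** SAP 7.1.1 by default keeps patients with missing data in percentage denominators, while SAP 7.1.5 says observed data without imputation. Suppose (an assumption, taken from the allowance of 24 − 22 = 2) that two of 24 have no Day 7 result and stay in the denominator as not cured. The cut-off is then 15 and must come from 22 patients: P(X ≥ 15 | 22, 0.70) = 67.1 %.

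**The case against.** The best reply is that 22 is no slip: it is the correct answer to a standard formula, and the documents never say that the sizing was exact. That is right about the origin. It makes the defect a mismatch between sizing method and analysis method, but the stated power is still wrong for the analysis that decides the trial.

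It can also be said that the two extra patients cover the gap. They do not. With all 24 evaluable the power is 84.7 %, and Protocol 9.3 has already assigned those two to non-evaluability. The mildest case is one patient lost: at n = 23 the miss risk is 12.0 %, and that case belongs in any range quoted.

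The synopsis can be read as a loose summary of Protocol 9.3, with 24 as the number enrolled. That reading is possible, so the inconsistency is minor. As worded, though, it attaches 90 % to 24, and that is not so under the exact rule either.

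The stronger objection concerns weight. The Protocol classes this as a feasibility investigation. The error cannot create a false success, and the interval, hypotheses and criterion are untouched. The 70 % is itself uncertain and unsourced in the sample-size text. At a true rate of 80 %, the figure Protocol 1.3.2 reports for a product it calls comparable, exact power is 98 % to 99 % for n = 22 to 24; cure definitions may differ, so this is context only. All of that stands, and it limits the practical severity without making the stated figure correct.

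**Conclusion.** The concern holds. At the planning values of 70 % against 40 %, one-sided 5 %, the Clopper-Pearson rule gives 81.4 % power with 22 evaluable patients, 88.0 % with 23 and 84.7 % with 24. The claimed 90 % is not reached at any of them. The risk of missing the primary objective is 12.0 % to 18.6 %, that is 1.2 to 1.9 times the implied 10 %. At the stated n of 22 the shortfall is 90 − 81.4 = 8.6 percentage points.

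The practical severity is moderate. Attained type I error is 2.1 % to 3.5 %, so a positive result is safe; what is understated is the chance of a false negative. These figures take patients without a Day 7 result out of the denominator. If they are kept in as not cured, power is lower, as the 67.1 % example shows.

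**What to change.** In Protocol 9.3, the synopsis and SAP 5.1, state the power for the exact interval: about 81 % with 22 evaluable patients, 88 % with 23 and 85 % with 24. Attach the headline figure to one n, the same in all three places, and say that 24 is the number enrolled. Name Clopper-Pearson as the basis of the calculation.

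Add the cut-offs to the criterion in SAP 7.9.1: at least 15 of 24, 14 of 23 or 14 of 22 cured. Say which denominator applies when a Day 7 result is missing, because SAP 7.1.1 and 7.1.5 point different ways. If all 24 dosed patients stay in the denominator, the cut-off is 15 whatever is missing.

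This costs wording and a less favourable stated power, with no extra patients and no change to the analysis. Should the sponsor want a true 90 %, the exact rule needs 25 evaluable patients, or at least 27 so that power does not dip below 90 % at 26, plus an allowance for non-evaluable patients.
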